7.6.2.1.3 DSP-5423P Treatment Period

1. Mean change in PANSS total score from the last evaluation before the initial application of DSP-5423P at each visit
2. Mean change in PANSS subscale scores from the last evaluation before the initial application of DSP-5423P at each visit
3. Mean change in PANSS five-factor model scores from the last evaluation before the initial application of DSP-5423P at each visit
4. Mean change in CGI-S score from the last evaluation before the initial application of DSP-5423P at each visit

Summary statistics for the variables (1) to (4) will be provided in tables and figures by visit and treatment group on the DSP-5423P dosed population. Only (1) and (4) will be repeated by country and race, however figures by race will not be needed.

The estimates of the change in the variables (1) to (4) obtained will be plotted by treatment group and visit with +/-SD

Summaries will be repeated for each PANSS item score in same manner, but Wilcoxon test for change from baseline to LOCF endpoint within each treatment group will be conducted additionally.

7.6.3 Sensitivity Analysis

This is described in the primary and secondary analyses section.

7.6.4 Subgroup Analysis

For the double-blind treatment phase:

Subgroup analysis will be performed for the mean change in PANSS total score and CGI-S score from baseline on the mITT population. The subgroup analysis will include sex, age, hospitalization status, antipsychotics use, and country. Age will be dichotomized as less than 65 years and older than or equal to 65 years. Subgroup analyses of before and after the interim analysis will also be performed where the before subgroup will consist of the subjects included in the interim analysis (1st to 251st randomized subjects) and the after subgroup consists of the remaining subjects. Antipsychotics use will be decided based on whether if subjects took any antipsychotics as prior medication or not. Antipsychotics will be identified up to Prior and Concomitant Medication category on CRF. Baseline characteristics and history of schizophrenia will also be summarized by before and after the interim analysis for the mITT and safety population.

For subgroup analyses by these variables other than country, inferential analysis of treatment-by-subgroup interaction at Week 6 will be performed for each subgroup variable using MMRM on the mITT population. The model will include fixed effects for treatment group, visit as a categorical variable, baseline score, pooled center, and treatment-by-visit treatment-by-subgroup, visit-by-subgroup, and treatment-by-subgroup-by-visit interactions. An unstructured covariance matrix will be used for the within-subject correlation and the Kenward-Rogers approximation will be used to calculate the denominator degree of freedom. In the case of a convergence problem with the unstructured covariance matrix, the following structures with a robust sandwich estimator for the standard error of the fixed effect estimates will be assessed in a sequential fashion: heterogeneous Toeplitz, heterogeneous first-order autoregressive, and Toeplitz.

Initial model:

```
proc mixed data = &ads;  
  class trt01p avisit site usubjid subgroup;  
  model chg = trt01p avisit site base subgroup trt01p*avisit  
trt01p*subgroup subgroup*avisit trt01p*subgroup*avisit/ DDFM=KR;  
  repeated avisit /type=UN subject=usubjid;  
  lsmeans trt01p*subgroup*avisit / diff cl alpha = 0.05;
```

run;

In case of non-convergence of the initial model:

```
proc mixed data = &ads empirical
  class trt01p avisit site usubjid subgroup;
  model chg = trt01p avisit site base subgroup trt01p*avisit
trt01p*subgroup subgroup*avisit trt01p*subgroup*avisit/ DDFM=KR;
  repeated avisit /type=TOEPH subject=usubjid;
  /* repeated avisit /type=ARH(1) subject=usubjid;*/
  /* repeated avisit /type=TOEP subject=usubjid;*/
  lsmeans trt01p*subgroup*avisit / diff cl alpha = 0.05;
run;
```

The subgroup analysis to be conducted by country or race will be performed using same MMRM model and options as the primary analysis detailed in 7.6.1., besides adjusted p-value, on the mITT population. The MMRM model will be applied by country or race respectively, not including subgroup factor like country or race into the mixed model as fixed factor.

In addition to analysis described above, PANSS total score and CGI-S and their change from baseline will be summarized by subgroup, visit (including LOCF endpoint), and treatment group for the mITT population.

DSP-5423P treatment period:

Subgroup analysis will be performed for the mean change in PANSS total score and CGI-S score from baseline. The subgroup analysis will include sex, age, hospitalization status, race, and country. PANSS total score and CGI-S score and their change from the on-treatment baselines will be summarized by subgroup, visit (including LOCF endpoint), and treatment group for the DSP-5423P dosed population.

7.7 Safety

Safety data will be listed.

7.7.1 Adverse Events

Treatment emergent AEs (TEAEs) are defined as follows:

- TEAEs (the double-blind treatment phase): Events with start date on or after the date of initial application of study drug in the double-blind treatment phase, and up to 17 days after the date of final application of study drug in the double-blind treatment phase and before the first application of DSP-5423P in the open-label treatment phase.
- TEAEs (DSP-5423P treatment period): Events with start date on or after the date of initial application of DSP-5423P either in the double-blind treatment period for 40MG and 80MG groups or in the open-label treatment period for placebo group and up to 17 days after the date of final application date of DSP-5423P.

AE with missing or incomplete start date after imputation will be considered as TEAE.

Treatment-related TEAE:

A treatment-related TEAE is defined as a TEAE for which the causal relationship to the study treatment is either 'definite', 'probable', or 'possible'.

Common TEAE:

Common TEAE in the double-blind treatment phase are PT of TEAEs experienced by 2% or more subjects in 40MG or 80MG group in the safety population.

Common TEAE in the DSP-5423P treatment period are PT of TEAEs experienced by 2% or more subjects in the overall-to-FLEX DOSE group in the DSP-5423P dosed population.

The summary of AEs will be limited to treatment-emergent AEs (TEAEs). The number and percentage of subjects with TEAEs during the double-blind treatment phase on the safety population and DSP-5423P treatment period on the DSP-5423P dosed population will be summarized by preferred term, system organ class, and treatment group. Summaries will be repeated by country and race.

Specifically, this will cover the following items:

- any TEAE;
- TEAE leading to death;
- TEAE leading to treatment discontinuation;
- serious TEAE;

- extrapyramidal TEAE;
- skin-related TEAE;
- treatment-related TEAE;
- treatment-related TEAE leading to death;
- treatment-related TEAE leading to treatment discontinuation;
- treatment-related serious TEAE;
- treatment-related extrapyramidal TEAE;
- treatment-related skin-related TEAE;

Skin-related TEAE is defined as the TEAE occurred at the application site (recoded in the CRF) and identified as TEAE with a wording “Application site” in MedDRA LLT.

The number and percentage of subjects reporting each TEAE will be summarized by system organ class (SOC) and preferred term (PT) for the double-blind treatment phase on the safety population and for the DSP-5423P treatment period on the DSP-5423P dosed population. Whenever appropriate, SOCs are sorted by alphabetically and PTs are sorted within SOC in descending order of frequency of the active group for the double-blind treatment phase and the Overall-to-FLEX DOSE group for the DSP-5423P treatment period. If there are ties, PTs are sorted by alphabetically. The following summaries will be produced for the double-blind treatment phase and DSP-5423P treatment period:

- TEAE by SOC and PT*;
- Common TEAE by PT#;
- treatment-related TEAE by SOC and PT;
- TEAE by maximum severity and PT;
 - This will be repeated for extrapyramidal TEAE and skin related TEAE
- TEAE leading to treatment discontinuation by SOC and PT+;
- Serious TEAE by SOC and PT;
- extrapyramidal TEAE by PT#+;
- skin related TEAE by PT#+;
- skin related TEAE by PT and application site;

Statistical Analysis Plan

Version: 2

Study No. D4904020

- TEAEs by first onset (Day 1 to 7, Day 8 to 14, Day 15 to 28, Day 29 or later), SOC and PT in the double-blind treatment phase;
 - This will be repeated for extrapyramidal TEAE and skin related TEAE
 - TEAEs by first onset (Week 1 to 6, 1 to 13, 14 to 26, 27 to 39, 40 to 52, 53 or later, Week 1=Day 1 to 7, Week 2=Day 8 to 14), SOC and PT in the DSP-5423P treatment period;
 - This will be repeated for extrapyramidal TEAE and skin related TEAE
 - TEAEs by DSP-5423P dose at onset (40MG, 60MG, 80MG), SOC and PT in the DSP-5423P treatment period;
 - TEAEs by modal daily dose (40MG, 60MG, 80MG), SOC and PT in the DSP-5423P treatment period;
 - TEAEs leading to dose reduced by SOC and PT in the DSP-5423P treatment period+;
 - TEAEs leading to dose increased by SOC and PT in the DSP-5423P treatment period+;
- * Summaries will be repeated by country and race. # Summaries will be repeated by country. +: listing will be produced.

In the above summaries, unless otherwise specified, if a subject experienced more than one episode of a TEAE within a PT or a SOC, the subject is counted only once in the PT or the SOC.

For summaries based on DSP-5423P treatment period and on-going event carried from DB phase, the following items will be handled as described. No handling will be applied for items not listed below;

- Serious TEAE: if the event is flagged as serious at least one time throughout DSP-5423P treatment period, the event will be summarized as Serious TEAE.
- Causality: Causality will be prioritized as listed in order, "DEFINITE", "PROBABLE", "POSSIBLE" and "NOT RELATED" in on-going event.
- Severity: Severity will be prioritized as listed in order, "SEVERE", "MODERATE", "POSSIBLE", "MILD" in on-going event.

Statistical Analysis Plan

Version: 2

Study No. D4904020

- Event leading to Dose Reduced: for on-going event, if the event is flagged as dose reduced in action taken at least one time throughout DSP-5423P treatment period, the event will be summarized as event concerned.
- Event leading to Dose Increased: for on-going event, if the event is flagged as dose increased in action taken, at least one time throughout DSP-5423P treatment period, the event will be summarized as event concerned.
- Application site: if on-going event have multiple application site throughout DSP-5423P treatment period, application site will not be prioritized, and the event will be counted per application site within associate PT.

For the summaries by maximum severity, if a subject experienced more than one episode of a TEAE within a PT, the subject is counted only once in the PT at the maximum severity. In determining maximum severity, severities are ranked from missing (not specified), mild, moderate, to severe. If the maximum severity is missing, the episode will be displayed as 'not specified'.

For the summaries of skin-related adverse events, if a subject experienced more than one episode of a TEAE within a PT for an application site of study drug, the subject is counted only once in the PT for the application site. If a subject had a PT occurred at different application sites, it will be counted per application site within associate PT.

For the summaries by first onset, if a subject experienced more than one episode of an TEAE within a PT, the subject is counted only once in the PT for the first episode. Denominator of percentage for each period of interest is the number of subjects who were treated with the study medication regardless of any suspensions of study medication between the initial and final date of application of study drug.

For the summaries by DSP-5423P dose at onset, if a subject experienced more than one episode of an TEAE within a PT, the subject is counted only once in the PT by DSP-5423P dose at onset. For example, if a subject has same PT twice but onset dose for each is not same, these PTs will appear one time each in different dose categories. Denominator of percentage for each dose is the number of subjects who have experienced the dose of interest at least once in the DSP-5423P treatment period in case that no DSP-5423P dose at onset is available, for example, the onset date is middle of prescribed periods or the onset date is after the final application, DSP-5423P dose at onset will be set to last non-missing dose taken at prior to the onset date.

No statistical comparisons of AEs between treatment groups will be performed.

Narrative of Serious AE will be produced by a subject who experienced SAE.

Hospitalization record will be listed.

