- f Discontinuation is defined as the last date of study drug application. The subject will undergo the discontinuation assessments within 5 days since the last date of study drug application.
- g Completion of treatment or discontinuation is defined as the last date of study drug application. The subject will undergo the follow-up assessments in 6 - 17 days since the last date of study drug application.

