### **6.3 Safety Endpoints**

- Adverse events (AEs) and adverse drug reactions (ADRs)
- Extrapyramidal AEs and ADRs
- Skin-related AEs and ADRs at the application site
- Assessment of skin irritation reaction at the application site
- Change in Drug-Induced Extrapyramidal Symptoms Scale (DIEPSS) total score (excluding overall severity) from baseline at Week 6
- Change in individual DIEPSS scores from baseline at Week 6
- Change in DIEPSS total score (excluding overall severity) from the last evaluation before the initial application of DSP-5423P at each visit
- Change in individual DIEPSS scores (excluding overall severity) from the last evaluation before the initial application of DSP-5423P at each visit
- Serum prolactin concentration
- Electrocardiogram (ECG) parameters (QTc)
- Concomitant use of antiparkinson drugs
- Assessment of suicide using Columbia-Suicide Severity Rating Scale (C-SSRS)
- Laboratory test values, vital signs, and body weight

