**Figure 1 Study Schematic**

## 7.2 Rationale

### 7.2.1 Rationale for the Study Design

The washout phase is designed to adequately evaluate the efficacy of DSP-5423P by excluding the placebo responders. Since placebo may worsen symptoms, the duration of the washout phase with placebo will be 1 week in principle, but must be at least 3 days. To evaluate long-term efficacy and safety, DSP-5423P will be applied as flexible dose in the open-label treatment phase. To evaluate the safety of a subject after completing or prematurely discontinuing the study drug, the follow-up observations will be performed in 1 to 2 weeks after completion or discontinuation of study treatment, despite the possibility of the study drug being replaced with other antipsychotics.

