**Table 10 Restrictions on concomitant medications/therapies**

	From screening before the washout phase	Washout phase	Double-blind treatment phase	Open-label treatment phase	Follow-up phase
Antipsychotics	B	A	A	B	C
Antimanic and antiepileptic drugs	A	A	A	B	C
MAO inhibitors	A	A	A	A	C
CYP3A4 inhibitors (External drugs for topical use can be used.)	A	A	A	A	A
CYP3A4 inducers (External drugs for topical use can be used.)	A	A	A	A	C
Adrenaline (excluding use for emergency treatment of anaphylaxis)	A	A	A	A	A
Other investigational products or post-marketed study products	A	A	A	A	A
Electroconvulsive therapy	A	A	A	A	C
Antiparkinson drugs	B	B	B	B	C
Psychotropic drugs (eg, anxiolytic drugs, antidepressants)	B	B	B	B	C
Hypnotic drugs	B	B	B	B	C
Treatments for complications	B	B	B	B	C

A, prohibited; B, restricted; C, unrestricted

Abbreviations: MAO=Monoamine oxidase; CYP3A4=Cytochrome P-450 enzyme 3A4

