### 10.3.1 Antipsychotics

Antipsychotics except for the study drug will be restricted as follows:

- For the subjects not treated with antipsychotics at screening  
Antipsychotics will be prohibited from screening until completion of assessments at the last visit (Visit 109 outside Japan or Visit 112 in Japan) of the open-label treatment phase or the discontinuation visit. If a subject completes the double-blind treatment phase and discontinues before entering the open-label treatment phase, antipsychotics will be prohibited until completion of assessments at Visit 6.
- For the subjects treated with any antipsychotics at screening  
The antipsychotics should be tapered and completely discontinued before the beginning of the washout phase. Antipsychotics will be prohibited from the beginning of the washout phase until completion of assessments at the last visit (Visit 109 outside Japan or Visit 112 in Japan) of the open-label treatment phase or the discontinuation visit. If a subject completes the double-blind treatment phase and discontinues before entering the open-label treatment phase, antipsychotics will be prohibited until completion of assessments at Visit 6.

If urgent treatment is required because of psychiatric symptoms such as acute psychomotor excitability during the open-label treatment phase, at the discretion of the Investigator, only one antipsychotic drug excluding depot neuroleptics and blonanserin can be used concomitantly on an as-needed basis. However, all antipsychotics will be prohibited within 48 hours before the PANSS, CGI-S, and C-SSRS assessments. The total duration of concomitant use of antipsychotics for urgent treatment during the open-label treatment phase should be 5 days or less outside Japan, and 10 days or less in Japan.

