## **12. SAFETY REPORTING**

### **12.1 Definitions**

#### **12.1.1 Adverse Events**

An adverse event (AE) is any untoward medical occurrence in a study subject administered a medicinal (investigational) product and which does not necessarily have a causal relationship with this treatment. An AE can, therefore, be any unfavorable and unintended sign (including an abnormal laboratory finding), symptom, or disease occurring after the administration of a medicinal (investigational) product, whether or not considered related to the medicinal (investigational) product. AEs may include the onset of new illness and the exacerbation of pre-existing conditions. AEs will be collected from the beginning of the study treatment in the washout phase until the follow-up visit. AEs also include other untoward events occurring from the beginning of the study treatment in the washout phase until the follow-up visit, for instance, events occurring in association with study-related procedures or assessments, or those occurring under placebo treatment.

AEs that occur during the washout phase and worsen during the double-blind treatment phase will be recorded as AEs in the washout phase and also as AEs in the double-blind treatment phase. AEs that occur during the washout phase and worsen during the open-label treatment phase will be recorded as AEs in the washout phase and also as AEs in the open-label treatment phase. The date of worsening will be

recorded as the onset date of the worsening AE. Likewise, AEs that occur during the double-blind treatment phase and worsen during the open-label treatment phase will be recorded as AEs in the double-blind treatment phase and also as AEs in the open-label treatment phase, with the date of worsening as the onset date. In addition, AEs that occur during the washout phase or double-blind treatment phase without further worsening in the following phase will be recorded as AEs in the washout phase or as AEs in the double-blind treatment phase, respectively.

Lack of efficacy may be an expected potential outcome and should not be reported as an AE unless the event is unusual in some way. New signs and symptoms of the underlying disease, or signs and symptoms of an emerging disease should be recorded as AEs.

The Investigator should attempt to establish a diagnosis of the event based on signs, symptoms, and/or other clinical information. In such cases, the diagnosis should be recorded as the AE and not the individual signs/symptoms.

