### **15.3.6 Safety Analysis**

#### **15.3.6.1 Adverse Events**

The summary of AEs will be limited to treatment-emergent AEs (TEAEs), which are defined as AEs with onset on or after Day 1. An ADR will be defined as an AE related to the study treatment; an AE of which causality with study drug is related, probably related, or possibly related.

The number and percentage of subjects with at least one AE or ADR in the double-blind treatment phase for each preferred term and system organ class will be summarized by treatment group. Also, the number and percentage of subjects with at least one AE or ADR developing after applying DSP-5423P during the entire study duration will be summarized overall and by treatment group. This summary will be repeated for death, SAEs, AEs leading to study discontinuation, severe AEs, extrapyramidal AEs, and skin-related AEs at the application site.

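### Double-blind TEAEs have a 17-day tail only for subjects who do not enter open label, and extrapyramidal events starting on a replacement antipsychotic in that tail are tabulated in the randomised arm without separation

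*SAP*

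**What the plan says.** SAP 7.7.1 starts the double-blind TEAE window at the first double-blind application and runs it "up to 17 days after the date of final application of study drug in the double-blind treatment phase and before the first application", where that application is the first patch of the open-label phase. Protocol 15.3.6.1 gives only a start: TEAEs, "which are defined as AEs with onset on or after Day 1". The 17 days match the follow-up visit (footnote to Protocol Table 4): "The subject will undergo the follow-up assessments in 6 - 17 days since the last date of study drug application". Protocol 12.1.1 sets the collection period: "AEs will be collected from the beginning of the study treatment in the washout phase until the follow-up visit".

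Protocol Table 10 uses the key "A, prohibited; B, restricted; C, unrestricted". It codes antipsychotics A in the double-blind phase and C in follow-up. Under Protocol 10.3.1 the ban for an early discontinuer ends once the discontinuation visit is done. For a completer who stops before open label, "antipsychotics will be prohibited until completion of assessments at Visit 6". Protocol 7.2.1 says that post-treatment safety is observed "despite the possibility of the study drug being replaced with other antipsychotics".

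Protocol 6.3 names "Extrapyramidal AEs and ADRs" as a safety endpoint. SAP 7.7.1 tabulates extrapyramidal TEAEs by treatment group, both all-cause and treatment-related, and plans no statistical comparison of AEs. It has no rule for an event that starts after another antipsychotic has been started.

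**The concern.** Whether a subject has a tail depends on what happened after randomisation: stopping early, or finishing and not continuing. Lack of efficacy and adverse events are both listed reasons for termination (Protocol 13.1). Replacement with another antipsychotic is foreseen in the same period. The double-blind extrapyramidal table can therefore mix events on the assigned patch with events on a different drug, and the mixing need not be equal across arms.

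At stake is how the drug-placebo extrapyramidal comparison is read, which serves the secondary objective of 6-week safety against placebo (Protocol 5.2). The plan is tighter for its other measures. Double-blind scale data stop 7 days after the final application (SAP 6.3 and 6.4), and concomitant medication, including antiparkinson drugs, counts only if it started by the final application (SAP 7.4.3). So an extrapyramidal TEAE in the tail can be counted while the antiparkinson drug started for it is not.

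**Working it through.** The plan gives no figure on this point, so there is none to reproduce. The check is of the windows, followed by an illustration.

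**Who has a tail.** Take a last double-blind patch on Day 42.
- Enters open label: the window closes at the first open-label application, about Day 42-43.
- Does not enter: the window runs to Day 42 + 17 = Day 59.

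**How much of the tail permits other antipsychotics.**
- The discontinuation visit falls 0-5 days after the last patch (Protocol 13.2), so 17 - 5 = 12 to 17 - 0 = 17 days of the defined window follow the end of the ban.
- AE collection ends at the follow-up visit, on day 6-17. For an early discontinuer, the time that is both unrestricted and observed runs from 6 - 5 = 1 day to 17 - 0 = 17 days.

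**Which tables are affected.** The all-cause extrapyramidal table has no causality filter. In the treatment-related table, *possible* counts as related (SAP 7.7.1), and Protocol 12.3 allows that rating where a concurrent drug could explain the event.

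**Illustration.** Let p be the on-treatment extrapyramidal risk, q the share not entering open label, and r the risk that a non-entrant both switches and has an observed extrapyramidal event in the tail.

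Reported risk = p + (1 - p) × q × r

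None of these values is in the documents. Assume p = 5% placebo and 12% active (risk ratio 2.40, difference 7.0 points) and r = 5%, 10% or 20%, the same in both arms.

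| q placebo / active | Risk ratio at r = 5 / 10 / 20% | Difference, points |
|---|---|---|
| 20% / 20% | 2.16 / 1.99 / 1.76 | 6.9 / 6.9 / 6.7 |
| 40% / 20% | 1.87 / 1.56 / 1.23 | 6.0 / 5.0 / 2.9 |
| 20% / 30% | 2.24 / 2.12 / 1.96 | 7.4 / 7.7 / 8.5 |

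Example, first row, r = 10%: placebo 0.05 + 0.95 × 0.20 × 0.10 = 0.069; active 0.12 + 0.88 × 0.20 × 0.10 = 0.1376; ratio 1.99; difference 6.9 points. With 167 per arm and q = 20%, the tail adds 1.6-6.3 placebo cases and 1.5-5.9 active cases over r = 5-20%.

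**Direction.** From the same formula:
- The difference grows if q active / q placebo exceeds 0.95 / 0.88 = 1.08, and shrinks below that.
- The ratio falls unless q active / q placebo exceeds 2.40 × 0.95 / 0.88 = 2.59.

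Under these assumptions, dilution of the ratio is the usual result, while the difference can readily move either way.

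**The case against.** The tail looks deliberate. Protocol 7.2.1 accepts replacement drugs as the price of observing safety after stopping, the 17 days match the follow-up visit, and counting all follow-up events in the assigned arm is a conventional inclusive choice. This stands, and it is why the existing table should stay.

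A reader might infer that such events enter without trace. They do not. SAP 7.7.1 produces a listing for extrapyramidal TEAEs, the double-blind medication listing in SAP 7.4.3 includes drugs taken after the final application, and the treatment-related table removes events rated not related. But matching two listings by hand does not make the table readable, and *possible* still counts as related.

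A reader might also infer that antipsychotics are unrestricted for all 17 days. Early discontinuers stay under the ban until their discontinuation visit, and AE collection may end as early as day 6.

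The extrapyramidal measure with planned between-group modelling, the DIEPSS total score, is largely protected: at the discontinuation visit it must be rated before other antipsychotics begin (Protocol Table 4, footnote e). What remains affected is one family of descriptive tables.

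Finally, cutting follow-up at the switch has its own bias, because subjects may switch because of adverse events or lack of efficacy. That counts against replacing the 17-day table, but not against adding a second one.

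**Conclusion.** The point holds as a gap in interpretability. The tail exists only for non-entrants, other antipsychotics become permitted within it, and no rule separates extrapyramidal TEAEs that start on them. If the true risk ratio is above 1, the tendency is to pull it towards 1.

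The stronger reading, that the drug will look more benign than it is, is not supported on the risk difference. That needs enough more non-entrants on placebo; with equal shares the difference barely moves, and with more non-entrants on active it grows. Discontinuation by arm, the switching rate and the extrapyramidal risk on replacement drugs are not in the documents, so the figures above show only how the mechanism works. They also assume the same r in both arms. No test, alpha or efficacy conclusion is touched.

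**What to change.** Keep the 17-day TEAE definition and its tables. Add to SAP 7.7.1:
- a double-blind extrapyramidal TEAE table by treatment group, limited to onset up to the earlier of the last application + 17 days and the day before the first non-study antipsychotic;
- a flag, in tables and listings, on any TEAE with onset on or after that start date.

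State that the first non-study antipsychotic means the first one started on or after Day 1, identified by the CRF category (SAP 6.7). SAP 6.5.2 sets a start date with a missing day to the first of the month, so list the subjects whose cut-off rests on an imputed date.

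The cost is one extra table and one date comparison; Protocol 10.3 already records medication start dates through the follow-up visit. The restricted table omits late study-drug events in subjects who switch quickly and ends follow-up at a post-randomisation event, so it should be read alongside the 17-day table. No visit, treatment or data-collection rule changes.
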